1.0 Project Summary/Abstract

[figure not shown]
Suicide is the second leading cause of death among female of reproductive age, and female suicide attempts occur most frequently around menses (perimenstrually), when estradiol (E2) and progesterone (P4) fall rapidly. A recent prospective study demonstrated that suicidal ideation (SI) and attempts peak perimenstrually in natural cycles, and that this perimenstrual worsening of SI can be prevented by administering stabilizing doses of E2+P4 (relative to placebo). Therefore, while E2+P4 withdrawal is a viable model of proximal suicide risk in females with SI, mechanisms are unclear. GABAergic neuroactive steroid metabolites of ovarian hormones (e.g., allopregnanolone), exert potent sedative and antidepressant effects; we hypothesize that acute perimenstrual withdrawal from these hormone metabolites may increase suicide risk by increasing hyperarousal and hopelessness. The **long-term objectives** of this research are to (1) use the menstrual cycle as a model to probe the proximal mechanisms of suicide, and (2) develop long-term treatments that eliminate hormonal contributions to suicide. The **objective of the current work** is to use a crossover placebo-controlled trial of E2+P4 stabilization (vs. natural E2+P4 withdrawal under placebo) in the perimenstrual weeks to probe behavioral (hopelessness, hyperarousal) and molecular/genetic (neuroactive steroid levels, mRNA expression for neurosteroidogenic enzymes) mediators of perimenstrual suicide risk. **Design:** In this mechanistic trial, 90 female outpatients with past-month SI will complete two counterbalanced conditions: (1) two weeks of placebo during natural perimenstrual E2+P4 withdrawal, and (2) two weeks of perimenstrual E2+P4 stabilization (.1mg/day transdermal estradiol + 200mg/day oral micronized progesterone) to prevent withdrawal. Five labs per condition will capture changes in GC-MS quantified neuroactive steroids and mRNA expression for neurosteroidogenic enzymes, and a wearable device (Oura Ring) will index basal body temperature and physiological arousal (heart rate, heart rate variability). Our app (*BiAffect*) will passively track arousal via movement and typing speed instability. 40 healthy controls (HC) with no SI will be recruited for a two-month long observational substudy, in which five lab visits across one menstrual cycle (timed identically to mirror the observations across one medication phase of the experimental trial) will capture baseline molecular/genetic changes for between-group comparisons. **Specific Aims.** Aim 1 is to evaluate hyperarousal and hopelessness as interacting mechanisms by which perimenstrual E2+P4 withdrawal (vs. experimental E2+P4 stabilization) increases proximal suicide risk. Aim 2 is to evaluate neuroactive steroid withdrawal as a mechanism by which perimenstrual E2+P4 withdrawal (vs. stabilization) increases proximal suicide risk. If appropriate, a multilevel path model will test a path in which E2+P4 withdrawal (vs. stabilization) causes neuroactive steroid withdrawal, which increases in hopelessness and hyperarousal, which in turn increases proximal suicide risk. Aim 3 (substudy) is to characterize GABA-A receptor gene expression plasticity across the cycle in individuals with and without perimenstrual changes in affect and suicide risk. **Relevance.** By conducting a mechanistic experiment to probe the mediators of a known cause of proximal suicide risk, the proposed research responds to public calls from the NIMH-sponsored Suicide Research Prioritization Agenda to identify modifiable causes of *proximal* suicide risk.

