We define **hyperarousal** (RDoC Arousal and Regulatory Systems) as (1) self-reported agitation and overwhelm, (2) psychomotor agitation (smartphone accelerometer instability/movement^{13,14}), (3) behavioral reactivity to external stimuli (smartphone typing speed instability^{13,14}, attentional bias toward angry/fearful faces on task¹⁵), and (4) physiological hyperarousal (reduced resting parasympathetic autonomic function¹⁶, increased sympathetic and decreased parasympathetic autonomic function during an emotionally arousing task).

[figure not shown]
We define **hopelessness** as a state of despair *arising due to repeated experiences of loss or sustained threat* (RDoC Negative Valence Systems). It will be measured primarily as self-reported hopelessness using the Beck Hopelessness Scale (BHS)¹⁷, and we will measure lifetime and daily exposure to loss and threat^{18,19}.

We define **proximal suicide risk** as the presence and severity of self-injurious thoughts and behaviors as assessed dimensionally using the Adult SI Questionnaire (ASIQ)²⁰ and categorically using the Self-Injurious Thoughts and Behaviors Interview -Revised (SITBI-R). These instruments assess for passive and active SI; suicide plans; aborted, interrupted, and actual suicide attempts; and suicide death. Although non-suicidal self-injury (NSSI) is a distinct but related phenomenon, we also consider NSSI as an index of proximal risk given its predictive validity for suicide attempt²¹.

[figure not shown]
Premise for Aim 1a

Perimenstrual Hormone Withdrawal Causes Proximal Suicide Risk

In the first prospective study¹² of daily suicide risk in females with SI (K99MH109667), the PI found that proximal suicide risk peaks perimenstrually, during periods of natural hormone (E2+P4) withdrawal (Fig. 3). 38 females with past-month SI completed daily ratings on the ASIQ²⁰ across a baseline menstrual cycle. ASIQ scores peaked during the perimenstrual weeks relative to late follicular week, $\gamma=-.88$, $p<.001$ and early luteal week, $\gamma=-.56$, $p<.001$. We also observed greater odds of endorsing suicidal planning items on perimenstrual vs. non-perimenstrual days (OR=4.29, $p<.001$). 28 of 30 participants reported the highest mean SI perimenstrually. *These data support the premise that suicide risk peaks perimenstrually.*

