3.0 Objectives/Aims

Our aim is to test the **central hypothesis** is that perimenstrual E2+P4 withdrawal induces rapid withdrawal from calming GABAergic neuroactive steroids, which in turn increases hyperarousal and hopelessness, which then interact to cause proximal suicide risk (Figure 1). P4 is metabolized to GABAergic neuroactive steroids, and E2 promotes expression of enzymes that convert P4 to neuroactive steroids⁹³. Perimenstrual E2+P4 withdrawal may increase suicide risk by causing rapid withdrawal from the antidepressant⁹ and sedative^{11,10} effects of neuroactive steroids⁹⁴, as well as withdrawal from the antidepressant effects of E2⁹⁵. Our preliminary experimental work strongly suggests that perimenstrual E2+P4 withdrawal (and neuroactive steroid withdrawal) heightens proximal suicide risk via hopelessness⁶⁵ and hyperarousal^{12,66}.

Figure 1. Peri-menstrual Hormone Withdrawal and Proximal Suicide Risk

Design: Using the PI’s hormone withdrawal paradigm (K99MH109667¹²), a new sample of 90 completers female outpatients with past-month SI will complete two counterbalanced conditions: (1) natural perimenstrual E2+P4 withdrawal (placebo), and (2) perimenstrual E2+P4 stabilization. Five labs per condition will capture changes in neuroactive steroids, mRNA expression for neurosteroidogenic enzymes, physiological arousal, behavioral indices of arousal, and interview/self-report indices of proximal suicide risk, hopelessness, and hyperarousal. Our app (BiAffect) will passively track indices of arousal including psychomotor agitation (accelerometer) and reactivity (typing speed variability). Additionally, Metricwire will passively track movement using smartphone sensors. 40 healthy controls (HC) will complete five labs across one observational cycle to characterize 1) normative cycle-related variation in neuroactive steroids and mRNA expression, and 2) group-related differences (i.e., past-month SI vs HC) in trajectories of GABAAR subunit change across the cycle.

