During the study, each participant will also wear an *Oura Ring*, a wearable ring device (that includes a pulse plethysmograph (PPG) and temperature sensors) throughout the study; these rings, which have been validated to index heart rate and heart rate variability (measures of physiological arousal), as well as changes in basal body temperature, will serve the dual purpose of measuring both physiological arousal and progesterone-related temperature changes across the cycle.

NOTE: A prior version of the protocols utilized lab-based measures of physiological arousal using a traditional EKG. However, given ongoing concerns regarding close contact during the COVID-19 pandemic, the NIMH program officer for the grant funding the present study has approved a change from lab-based cardiovascular physiological recording using EKG to ambulatory assessment of physiological arousal using the Oura Ring.

Repeated Laboratory Visits for HC participants (Aim 3 substudy)

HC participants will complete 5 60-minute lab visits across one menstrual cycle. Repeated lab visits will be timed identically in the HC substudy group as in the primary group (i.e., 5 lab visits scheduled on days +7, +10, +14, +18, and +22 relative to a positive urine ovulation test. Participants will undergo a blood draw, urine pregnancy and standard drug screen (day +7), and report health behaviors and illness. Participants will **not receive any experimental patch application**, will not complete cognitive tasks, and will not complete interviews.

Debriefing Visit (1 hour)

After completing both randomized conditions, participants will be asked to attend for a 1 hour debriefing session with [name] either in-person or virtually in which participants will be unblinded, learn more about the purpose of the study, have any concerns or questions participants may have about the study answered and addressed, and evaluate the participant's current risk of suicide upon study completion.

Debriefing Visit for HC participants (Aim 3substudy)

HC participants will not be asked to attend a debriefing session, as they do not complete randomized double-blind experimental conditions, and they do not have suicide risk to assess.

CLINICAL LABORATORY ASSESSMENTS AND SAMPLING:

A point-of-care urine pregnancy test will be completed in our laboratory on site at the first visit of both conditions. A positive pregnancy test will result in termination of participation and will be managed by [name].

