Self-Reports. Self-report **surveys** from the enrollment visit will be repeated at each laboratory visit, with instructions to report symptoms in the past week or since the last visit. The "since last visit" version of the C-SSRS¹⁰⁴ **interview** will be used to precisely measure discrete self-injurious thoughts and behaviors at each laboratory visit; responses will be coded into suicide outcomes using the C-CASA⁹⁸.

We will operationalize behavioral hyperarousal (reactivity) as a longer response time when matching emotional faces relative to shapes. We will utilize these measures as independent predictors of proximal suicide risk, as well as variables with which to further validate *BiAffect* indices (below).

Physiological Arousal. Following the laboratory visit, participants will be mailed an Oura Ring in the appropriate size, along with instructions for charging and use, and asked to wear the ring as much as possible while in the study. This commercially available product is intended for fitness tracking and recreational use. It is worn on the middle finger and also uses PPG technology along with mechanical sensors to measure physical activity, sedentary behaviors, sleep, heart rate, oxygen saturation, and body temperature.

Participants will also be asked to use the Oura app- this commercially available application is required to collect data from supported Oura products. It is publically and free available for both Android and iOS devices in their respective app stores. Data from the Oura Ring will be transferred to the Oura smartphone app, and later to the Oura cloud storage service (where it can be retrieved later by the study team) using an Oura Ring app account created by the study team using the participant's confidential study email address (e.g., [contact]). Data collected and uploaded to the cloud will not include IP address or any other participant-identifying information.

Self-reports and physiological arousal for HC participants (Aim 3 substudy).

HC participants will not be asked to complete self-report surveys or cognitive tasks at laboratory visits. They will not wear an Oura Ring or use the Oura app.

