Behavioral Reactivity to External Stimuli: Typing speed instability will be calculated as a momentary and daily measure of reactivity to phone-based stimuli. Instability metrics will be calculated as the root mean square successive difference (rMSSD). This metric evaluates variability in consecutively recorded typing speeds and encapsulates both the size and the temporal order of within-subject fluctuations. In a prior study, our team has demonstrated that daily typing instability is able to prospectively predict disturbed mood¹²².

A variety of other relevant indices will be available from the BiAffect Keyboard, including but not limited to the number of errors made while typing, diurnal activity patterns and inferred hours of sleep, and amount of phone usage¹²³.

Physiological Arousal: Oura Ring Devices will collect data on the subject's body temperature, heart rate, interbeat interval) of sufficient quality for heart rate (HR) and heart rate variability (HRV) analysis.

Metricwire is a multi-platform (iOS and Android) smartphone app (www.metricwire.com) that has been previously used in many health and behavioral studies. Participants who have a compatible mobile device will be emailed a link and given a lab-generated email and password to sign up for the study. The app is used for a variety of methods in the literature; here, it will be used as an adjunct application to capture accelerometer and movement data from the smartphone's sensors. This is being collected in addition to the movement data from BiAffect since the sampling rate is higher and it can collect data even when the participant is not typing. Metricwire data will be collected up until July 31st, 2023. After this date, participants will no longer be enrolled into the Metricwire app and no data will be collected.

Smartphone-based assessments for HC participants (Aim 3 substudy).

HC participants will complete the following as described above: daily symptoms survey, BiAffect app (psychomotor changes, behavioral reactivity to external stimuli), Metricwire. HC participants will **not** receive Oura rings for physiological arousal.

Participant Compensation.

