2. **For laboratory visit outcomes**, we will again utilize multilevel models (with 10 labs per person—5 per condition—nested within individuals; two-level models). A two-level model will predict each repeated measures lab outcome from covariates (daily pain, illness, PRN medication use) and the interaction between (1) **experimental condition** (a dichotomous variable coded as 0 for natural hormone withdrawal condition and 1 for hormone stabilization condition) and (2) **condition phase**, a categorical (contrast) variable coded as follows: *midluteal baseline visit*, *perimenstrual experimental visit*, and the *medication withdrawal visit*. **Number of lab observations per person.** For the primary contrast between the midluteal and perimenstrual experimental phases, there are 4 observations per person—2 per condition. Based on our preliminary data from the K99 trial (identical experimental manipulation), we anticipate very minimal missing laboratory data (see grant for details) but have estimated that on average each completer participant will miss .25 visits.
3. **Hypothesized Pattern of Effects for Daily and Lab outcomes:** A significant interaction between experimental condition and condition phase is hypothesized for all twelve specified outcomes such that, in the natural withdrawal condition we expect deleterious changes from the midluteal phase to the premenstrual and menstrual phases (due to corresponding hormone withdrawal), but in the hormone stabilization condition we expect no deleterious changes (or less severe changes) from the midluteal to the premenstrual and menstrual phases (since hormone withdrawal is prevented).

Testing Associations Between Mediators and Suicide Outcomes: Aim 1 and 2 next require that we evaluate the day-to-day or week-to-week associations between single mediators (listed above) and suicide outcome variables on the same day or visit. This will be carried out in similar multilevel models as above, predicting each of the three primary suicide outcomes from person-centered values for each of the 9 mediators (listed above).

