- Aim 1 Mediation Outcomes (for Mediation by Hopelessness, Arousal). Aim 1 focuses on mediation of our experimental effects by hopelessness, hyperarousal, and their interaction. The primary hopelessness outcome will be (4) daily hopelessness on items from the Beck Hopelessness Scale (validated against full BHS in the laboratory; ICC=.32 in K99 trial). The primary arousal outcomes will be (5) daily hyperarousal as measured with the Brief Agitation Measure (validated against POMS Arousal subscale in the laboratory; ICC=.26 in K99 trial), (6) daily total smartphone accelerometer displacement reflecting overall locomotor activity (measured continuously using our BiAffect app, per reviewer recommendation; ICC=.54 in Co-I [name]'s prior study in patients with bipolar disorder), and (7) daily average typing speed instability reflecting greater reactivity to external stimuli (measured using our Biaffect App; ICC=.38 in Co-I [name]'s prior study in patients with bipolar disorder), (8) degree of RSA withdrawal during the Face Matching Task (no ICC estimate available for repeated administration; we assume a moderate ICC between .4-.6), and (9) degree of PEP shortening during the Face Matching Task (no ICC estimate available for repeated administration; we assume a moderate ICC between .4-.6).
- Aim 2 Mediation Variables (Mediation by Neurosteroids and Neurosteroidogenic Enzymes). Aim 2 focuses on mediation of our experimental effects by neuroactive steroid levels and mRNA expression for neurosteroidogenic enzymes. The primary outcomes will be (10) levels of allopregnanolone as measured using GC-MS; average ICC of .29 in former K99 mentor's prior trials with 4 measures across the cycle in naturally cycling women), (11) gene expression for 5a-RI (no ICC estimate available for repeated administration; we assume a moderate ICC between .4-.6)., and (12) gene expression for 3a-HSDII.

ANALYTIC STEPS

Specification of Steps for Analytic Plan:

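### SAP outcome 9 (PEP shortening) has lost its data source and outcome 8 (RSA withdrawal) cannot be analysed as defined since the Oura Ring replaced the lab EKG; the lab rows of the SAP power tables also need reconciling

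*SAP*

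**What the plan says.** **SAP, Outcome Specification.** There are three suicide outcomes and nine mediators. Outcome 8 is "8) degree of RSA withdrawal during the Face Matching Task (no ICC estimate available for repeated administration"; outcome 9 is PEP shortening during the same task. For both, the SAP assumes an ICC between .4 and .6. Each has a row in the main power table and in the supplemental table.

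**Protocol Section 6.0, note under Repeated Laboratory Visits.** The NIMH program officer "has approved a change from lab-based cardiovascular physiological recording using EKG to ambulatory assessment of physiological arousal using the Oura Ring".

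**What the ring is said to give.** In Section 1.0, "a wearable device (Oura Ring) will index basal body temperature and physiological arousal (heart rate, heart rate variability"; in Section 6.0, "interbeat interval) of sufficient quality for heart rate (HR) and heart rate variability (HRV) analysis".

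**What the face task is said to give.** Section 6.0: "We will operationalize behavioral hyperarousal (reactivity) as a longer response time when matching emotional faces relative to shapes". No other readout of the task is described there.

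**Text not brought into line.** Section 2.0 still defines physiological hyperarousal partly as "increased sympathetic and decreased parasympathetic autonomic function during an emotionally arousing task". Section 3.0 still says "Five labs per condition will capture changes in neuroactive steroids, mRNA expression for neurosteroidogenic enzymes, physiological arousal, behavioral indices of arousal". Section 10.0 still refers to nine mediators and states "A significant interaction between experimental condition and condition phase is hypothesized for all twelve specified outcomes". It names no Oura variable.

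**The concern.** A pre-specified outcome needs a measurement, a time window and a rule for turning the recording into a number. After the change of device, outcome 9 has none of these in the documents. Outcome 8 has a possible sensor but neither of the other two. They are two of the six Aim 1 mediators (outcomes 4 to 9) and the only two that are cardiac.

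Heart rate and HRV are named as the replacement constructs, but no summary, window or model is fixed for them. Section 10.0 constructs a mediation interval only after the experimental effects and the mediator-outcome association have proved significant, so a mediator left undefined until then could be chosen with results in view. Participants are also unblinded one at a time at debriefing. The definition should therefore be fixed before outcome data are analysed by condition.

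A second, smaller matter is that the SAP's two power tables treat the lab outcomes inconsistently.

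**Working it through.** **1. Data source.** This step needs no arithmetic.

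| Outcome | Needed as defined | Described in the current protocol |
|---|---|---|
| 8, RSA withdrawal in the task | Cardiac recording during the task, and a rule for the change | Ring worn during the study, giving interbeat interval and HRV; no task window, no rule |
| 9, PEP shortening in the task | A PEP recording during the task | PEP is not among the ring's listed outputs; no other device is named |

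Section 10.0 names neither RSA nor PEP. Its totals do agree with the SAP list, 3 + 9 = 12, and that sum is reached only if outcomes 8 and 9 are included.

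**2. Reproducing the SAP's power method.** Inputs from the SAP power section: n = 85 completers, f² = .10, three predictors, one-tailed alpha .004. Observations per person, m, are 24 for daily outcomes and 4 − .25 = 3.75 for lab outcomes (four visits in the primary contrast, less the expected missing visits).

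Effective N = n × m / (1 + (m − 1) × ICC). Power is taken from the noncentral t distribution with df = N − 4 and noncentrality √(f² × N).

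- Suicidal ideation, ICC .64, m = 24: 2040 / 15.72 = 129.8, power .816. The SAP gives 130 and .81.
- PEP, ICC .50, m = 3.75: 318.75 / 2.375 = 134.2, power .832. The SAP gives 134 and .83.

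The method reproduces both rows.

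**3. The HRV row.** It is marked as a lab measure with ICC .50, but shows 163 and .90.

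- Lab basis, m = 3.75: 134.2 and .832, identical to the PEP row.
- Daily basis, m = 24: 2040 / 12.5 = 163.2 and .910.

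The printed figure matches the daily count.

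**4. The supplemental table.** At alpha .004, 80% power needs an effective N of 126 (power .801). Participants needed = 126 × (1 + (m − 1) × ICC) / m.

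| Lab outcome | m = 5.75 | m = 3.75 | Table prints |
|---|---|---|---|
| ICC .50 | 73.96, so 74 | 79.8, so 80 | 74 |
| Allopregnanolone, ICC .29 | 52.1, so 53 | 60.4, so 61 | 53 |

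The supplemental table fits 5.75 visits, which is the SAP's six-lab model less .25. The main table fits 3.75.

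**5. The ICC range.** The inputs to the lab power figure call .50 the largest expected lab ICC, whereas Outcome Specification assumes .4 to .6 for outcomes 8, 9 and 11. With m = 3.75 and alpha .004:

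| ICC | Effective N at 85 | Power at 85 | Effective N at 90 | Power at 90 |
|---|---|---|---|---|
| .4 | 151.8 | .884 | 160.7 | .905 |
| .5 | 134.2 | .832 | 142.1 | .858 |
| .6 | 120.3 | .777 | 127.4 | .807 |

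At ICC .6 the number needed is 126 × 2.65 / 3.75 = 89.04, so 90.

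**6. Alpha.** .05/12 = .0042, used as .004. With both outcomes withdrawn, .05/10 = .005, and suicidal ideation power at 85 moves from .816 to .836. With only outcome 9 withdrawn, .05/11 = .0045, and that power is .828.

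**The case against.** The strongest reply is that the SAP simply predates a disclosed, approved change made because of the pandemic. The protocol records the change openly and names heart rate and HRV in place of the old measures. That is fair on motive and transparency. It does not settle the analysis, because the mismatch lies in current protocol text and in the only SAP supplied, and no Oura summary has been specified.

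Four stronger readings are tempting and should be resisted.

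- *Outcome 8 has no sensor.* The documents do not show this. The ring is worn throughout the study, tasks are done at lab visits, and nothing says that it is removed there. The gap is the window and the derivation rule, which is milder than the gap for PEP.
- *Section 10.0 explicitly tests RSA and PEP.* It does not name them. They are included only through the counts.
- *The trial is underpowered for lab outcomes at ICC .6.* That holds at the SAP's 85 completers (.78), but the protocol plans 90 (Sections 3.0 to 6.0), where power is .81.
- *The supplemental table is miscalculated for lab outcomes.* Its 74 and 53 are consistent with the six labs per person in the SAP's lab model. What is wrong is that the two tables use different bases without saying so.

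One caution about the supplemental table stands. The formula in step 4 with m = 24 does not return three of its daily rows: it gives 60, 20 and 44 for planning, attempt and hopelessness, against 57, 21 and 45 printed. The table is therefore better regenerated than patched.

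**Conclusion.** The point holds and should be fixed. Two of nine mediators (two of twelve outcomes) cannot be analysed as pre-specified: outcome 9 for want of any data source, outcome 8 for want of a task-locked window and a derivation rule. The suicide outcomes and arousal outcomes 5 to 7 are untouched. Withdrawing the two outcomes costs no power elsewhere, and keeping alpha at .004 would only be conservative.

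In the main power table, the HRV row overstates lab power, at .90 against .83. The supplemental lab rows become 80 and 61 on the main table's basis, both below 85 and 90. The planned size therefore stands at ICC .50 and, with 90 completers, also at .60.

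The power figures rest on the SAP's own design-effect method, its f² of .10, its one-tailed alpha of .004 and 3.75 lab observations per person. The data-source finding rests on the supplied documents alone. A later SAP that defines Oura outcomes would answer it.

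**What to change.** Before outcome data are analysed by condition, amend the SAP and Protocol Section 10.0 as follows.

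1. Withdraw outcome 9.
2. Either withdraw outcome 8, or replace it with one named Oura heart rate or HRV summary, with a fixed time window, in the daily model. If it is kept as a lab outcome, describe the recording during the task and the derivation rule, and correct its main-table row to 134 and .83.
3. Restate the mediator and outcome counts and the Bonferroni alpha: .05/10 = .005 if both go, .05/11 = .0045 if only outcome 9 goes, or .004 retained and described as conservative.
4. Bring the definition of hyperarousal in Section 2.0 and the design paragraph in Section 3.0 into line with the ring-based measurement.
5. Put both power tables on one stated number of lab observations per person, regenerate the supplemental table, and show lab power at ICC .4, .5 and .6 for the current target of 90 completers.

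The cost is a SAP amendment and edits to three protocol sections. Withdrawal or replacement by a ring summary needs no new visit, device or procedure. Keeping outcome 8 in the lab could need an added recording procedure, since none is described.
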